13. SPECIMEN BANKING

- *If specimens will be banked for future research, describe where the specimens will be stored, how long they will be stored, how they will be accessed and who will have access to the specimens*
- *List the information that will be stored with each specimen, including how specimens are labeled/coded*
- *Describe the procedures to release the specimens, including: the process to request release, approvals required for release, who can obtain the specimens, and the information to be provided with the specimens.*

N/A

14. DATA MANAGEMENT AND CONFIDENTIALITY

- *Describe the data and specimens to be sent out or received. As applicable, describe:*
 - *What information will be included in that data or associated with the specimens?*
 - *Where and how data and specimens will be stored?*
 - *How long the data will be stored?*
 - *Who will have access to the data?*
 - *Who is responsible for receipt or transmission of data and specimens?*
- *Describe the steps that will be taken to secure the data during storage, use and transmission.*

Data will be obtained from the medical electronic records and tabulated in REDCap using adequate patient de-identifiers to avoid HIPAA violations. Only research staff (i.e. principal investigator, co-investigators and research coordinators) will have access to the database. The data will be stored up as required by regulatory guidelines.

Data is only being stored on REDCap which would be accessed only from a hospital computer. Only de-identified data will be exported and transmitted, minimizing risk of breaching patient confidentiality. All paper consent forms will be locked securely at [name].

15. DATA AND SAFETY MONITORING PLAN

A specific data and safety monitoring plan is only required for greater than minimal risk research. For guidance on creating this plan, please see the [Guidance Document](#) on the HRPP website.

Part I – this part should be completed for all studies that require a DSMP.
Part II – This part should be completed when your study needs a Data and Safety Monitoring Board or Committee (DSMB/C) as part of your Data and Safety Monitoring Plan.

Part I: Elements of the Data and Safety Monitoring Plan

- *Indicate who will perform the data and safety monitoring for this study.*
- *Justify your choice of monitor, in terms of assessed risk to the research subject's health and well being. In studies where the monitor is independent of the study staff, indicate the individual's credentials, relationship to the PI, and rationale for selection*
- *List the specific items that will be monitored for safety (e.g. adverse events, protocol compliance, etc)*
- *Indicate the frequency at which accumulated safety and data information (items listed in # above) will be reviewed by the monitor (s) or the DSMB/C.*
- *Where applicable, describe rules which will guide interruption or alteration of the study design.*
- *Where applicable, indicate dose selection procedures that will be used to minimize toxicity.*
- *Should a temporary or permanent suspension of your study occur, in addition to the IRB, indicate to whom will you report the occurrence.*

Data and safety monitoring will be performed after the first 20 patients are enrolled in the study. Subsequent monitoring will occur when 50 and 100 patients are recruited. A designated committee from the study will be assigned for this purpose, and potential side effects such as secondary bacterial and fungal infections, as well as, clinically significant hyperglycemia as defined above will be assessed.

Part II: Data and Safety Monitoring Board or Committee

- *When appropriate, attach a description of the DSMB.*
- *Provide the number of members and area of professional expertise.*
- *Provide confirmation that the members of the board are all independent of the study.*

The DSMB is not an independent committee and includes coinvestigators who are not part of the consenting process, made up of senior faculty members who are familiar with the protocol and have had prior clinical research experience.

16. WITHDRAWAL OF SUBJECTS

- *Describe anticipated circumstances under which subjects will be withdrawn from the research without their consent*
- *Describe procedures for orderly termination*
- *Describe procedures that will be followed when subjects withdraw from the research, including partial withdrawal from procedures with continued data collection.*

Patients may choose to withdraw from the study at any time. They will be asked to provide a reason for withdrawal if they choose to and will be asked if investigators can follow the electronic health record data over time until the study is completed.

Participants may be withdrawn from the study if deemed appropriate by clinician judgement. Data will be analyzed as intention-to-treat.

17. RISKS TO SUBJECTS

- *Describe any potential risks and discomforts to the subject (physical, psychological, social, legal, or other) and assess their likelihood and seriousness and whether side effects are reversible. Where appropriate, describe alternative treatments and procedures that might be advantageous to the subjects.*
- *Include risks to others, like sexual partners (if appropriate)*
- *Discuss why the risks to subjects are reasonable in relation to the anticipated benefits and in relation to the importance of the knowledge that may reasonably be expected to results*
- *Describe the procedures for protecting against or minimizing any potential risks, including risks to confidentiality, and assess their likely effectiveness.*

Potential risks for the patients in the higher dexamethasone dose group include but are not limited to higher risk of hyperglycemia, delirium and bacterial or fungal infections. Most of these side effects are treatable and reversible. To minimize any potential risks, patients will be monitored for signs or symptoms suggestive of secondary infections, so they can be identified and treated early. Glucose levels will be checked as part of routine medical care to ensure adequate control of hyperglycemia. For patients who develop delirium, use of non-pharmacological and pharmacological interventions will be offered based on clinical judgment. These risks are reasonable in relation to the potential benefits and importance of knowledge that can be obtained with the results of the study. A data and safety monitoring committee will be created to assess for the development of adverse events.

18. RESEARCH RELATED HARM/INJURY

- *Describe the availability of medical or psychological resources that subjects might need as a result of anticipated problems that may be known to be associated with the research.*
- *If the research is greater than minimal risk, explain any medical treatments that are available if research-related injury occurs, who will provide it, what will be provided, and who will pay for it.*

If adverse events occur, they will be handled as per routine clinical care protocols (i.e. treatment of hyperglycemia and infection).

19. POTENTIAL BENEFIT TO SUBJECTS

- *Explain what benefits might be derived from participation in the study, noting in particular the benefit over standard treatment (e.g. a once-a-day administration instead of four times a day, an oral formulation over an IV administration).*
- *Also state if there are no known benefits to subjects, but detail the value of knowledge to be gained*

Benefits to participants include enrollment in a study that will help answer questions regarding the optimal dosage of steroids in COVID-19 patients to help improve clinical outcomes and potentially a mortality benefit.

20. PROVISIONS TO PROTECT PRIVACY INTERESTS OF SUBJECTS

- *Describe the methods used to identify potential research subjects, obtain consent and gather information about subjects to ensure that their privacy is not invaded.*
- *In addition consider privacy protections that may be needed due to communications with subjects (such as phone messages or mail).*

Potential research subjects will be screened via Sunrise. Investigators will review the oxygen saturation and oxygen requirements of patients admitted to the COVID floors and review for eligibility. For patients who are discharged prior to 28 days, a survey will be sent out via email using REDCap to determine primary endpoint and subjective symptoms. Only relevant information will be collected and stored directly into REDCap. For patients without access to email or who do not respond to the survey, a follow up phone call will be made. Only information relevant to the research will be reviewed to ensure patient privacy.

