9. STUDY TIMELINES

- *Describe the duration of an individual's participation in the study*
- *Describe the duration anticipated to enroll all study subjects*
- *The estimated date of study completion*

The duration of an individual's participation in the study will be 28 days or until hospital discharge, whichever occurs first.

The duration anticipated to enroll all study subjects is 6 months.

The estimated date of study completion is 12 months.

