10. ENDPOINTS

- *Describe the primary and secondary study endpoints*
- *Describe any primary or secondary safety endpoints*

Primary study endpoint: all-cause mortality at 28 days.

Secondary study endpoints: need for ICU admission, ICU length of stay, hospital length of stay, higher requirements of oxygen supplementation (venturi mask, non-rebreather mask, high-flow nasal cannula or non-invasive mechanical ventilation), invasive mechanical ventilation, duration of invasive mechanical ventilation, ECMO, tracheostomy, subjective symptoms at 28 days, disposition upon discharge, and oxygen supplementation upon discharge.

The primary and secondary safety endpoints will include the development of secondary bacterial or fungal infections that is objectively identified based on culture data, and clinically significant hyperglycemia requiring ICU stay or insulin drip.

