11. RESEARCH PROCEDURES

- *Include a detailed description of all procedures to be performed on the research subject and the schedule for each procedure.*
- *Include any screening procedures for eligibility and/or baseline diagnostic tests*
- *Include procedures being performed to monitor subjects for safety or minimize risks*
- *Include information about drug washout periods*
- *If drugs or biologics are being administered provide information on dosing and route of administration*
- *Clearly indicate which procedures are only being conducted for research purposes.*
- *If any specimens will be used for this research, explain whether they are being collected specifically for research purposes.*
- *Describe any source records that will be used to collect data about subjects*
- *Indicate the data to be collected, including long term follow-up*

All hospitalized patients with COVID-19 infection documented by a positive PCR test who require oxygen supplementation or have documented hypoxemia based on oxygen saturation <94% will be screened for eligibility. Baseline diagnostics tests will be as per standard of care and no additional testing is required for our research purposes. All patients will receive routine medical care as per most updated COVID-19 guidelines prior to randomization.

Eligible patients who agree to participate in the study will be randomized 1:1 into two groups. Randomization was set up in REDCap. Once the patient gives consent, the randomization form on REDCap will randomize to either of the groups. As the study is multi-site, the randomization will be stratified by each site.

The standard dexamethasone group will receive a dose of 6 mg daily. The higher dexamethasone group will receive a dose of 0.2 mg/kg/day with maximum dose of 20 mg per day. The route of administration will be IV for both groups. No patients will receive less than dexamethasone 6 mg. The duration of treatment in both arms will be a total of 10 days of steroids or until discharge, whichever comes first.

No procedures, blood draws, imaging or diagnostic testing will be performed on the participants other than those indicated for their medical care.

Data will be obtained from the medical electronic records and tabulated in REDCap. Patient will be de-identified and REDCap access will be limited to appropriate investigators involved in the trial to avoid HIPAA violations.

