Sample size consideration: The sample size calculation was based on the hypothesis of primary endpoint. Our primary hypothesis is that the use of a higher dose of dexamethasone equivalent to 1 mg/kg/day of methylprednisolone would be associated with a decrease in mortality in COVID-19 patients requiring oxygen supplementation. A two group χ^2 test with a 5% two-sided significance level will have 80% power to detect the difference between the proportion of dexamethasone 6 mg group 23.3% and the proportion of dexamethasone weight based 5.9% (odds ratio of 0.206) when the sample size in each group is 64.

To account for 10% dropout rate, will be increasing recruitment to 142, with 71 in each arm to ensure 128 evaluable subjects.

Missing data: If there is less than 5% of an endpoint missing, complete case analysis will be used; if there is more than 5% missing, sensitivity analysis will be performed by assuming all the missing values of an endpoint to be either outcome if it is binary, or by assuming all the missing values of an endpoint to be either upper quartile or lower quartile of the available values if it is continuous, to see if the results are similar to those using complete case analysis.

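### After discharge, day-28 vital status depends on the patient answering an email or a phone call, so deaths between discharge and day 28 are at risk of being selectively missing

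*Combined protocol and SAP*

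**What the plan says.** Section 10 sets the endpoint: "Primary study endpoint: all-cause mortality at 28 days". For patients who leave hospital before day 28, the only procedure assigned to it is in section 20 (Provisions to Protect Privacy Interests of Subjects): "a survey will be sent out via email using REDCap to determine primary endpoint and subjective symptoms". The backup follows: "For patients without access to email or who do not respond to the survey, a follow up phone call will be made". The section does not say who may answer that call, how many attempts are made, or how an unreached patient is classified.

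Four other places bear on the point:

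- Section 11 (Research Procedures) gives the general data source: "Data will be obtained from the medical electronic records and tabulated in REDCap". It sets no vital-status check at day 28.
- Section 16 (Withdrawal of Subjects) provides for later record follow-up, but only for patients who withdraw, who "will be asked if investigators can follow the electronic health record data over time until the study is completed".
- Section 9 (Study Timelines) gives the length of participation as "28 days or until hospital discharge, whichever occurs first". This does not agree with contacting discharged patients about day 28.
- Section 12 (Statistical Analysis, missing data) says: "If there is less than 5% of an endpoint missing, complete case analysis will be used". Above 5%, a sensitivity analysis sets all missing binary values to one outcome or the other.

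**The concern.** A patient who has died cannot complete the survey or take the call. If no one else reports the death, the outcome is missing because of its own value. Complete-case analysis then removes that patient from both numerator and denominator, and the observed data cannot show that this has happened.

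Only deaths between discharge and day 28 are exposed, since deaths in hospital are known. But the trial expects few deaths, especially in the higher-dose arm, so one or two missed events can move the primary comparison. Randomisation does not protect against this if the arms differ in late deaths or in how reachable their discharged patients are.

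**Working it through.** **Inputs from the documents.** Planned 28-day mortality 23.3% (6 mg) and 5.9% (weight-based); 64 evaluable per arm; 142 recruited, 71 per arm; two-sided 5% test, 80% power; chi-squared or Fisher's exact test; 5% missing-data threshold (sections 8 and 12).

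**Inputs not in the documents.** The share of deaths that occur after discharge (s), the fraction of those missed (m), and the fraction of survivors lost (a). These are assumed below: s from 10% to 30%, m from 10% to 100%, a from 5% to 10%.

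**1. The plan's own sample size.** With pooled variance and no continuity correction,
n = [1.960·√(2·0.146·0.854) + 0.842·√(0.233·0.767 + 0.059·0.941)]² / 0.174² = (0.979 + 0.407)² / 0.0303 ≈ 63.5, so 64 per arm. Power at 64 is 80.3%. The figure reproduces and is not in dispute.

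**2. Unknown outcomes against expected deaths.** Expected deaths at 71 per arm are 71 × 0.233 = 16.5 and 71 × 0.059 = 4.2. The threshold is 0.05 × 142 = 7.1, so 7 unknown outcomes (7/142 = 4.9%) fall below it and get no sensitivity analysis. Seven exceeds the deaths expected in the higher-dose arm.

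**3. Direction of bias in observed mortality.** With true mortality p, a complete-case analysis observes
p(1 − s·m) / [p(1 − s·m) + (1 − p)(1 − a)].
This is below p only when s·m exceeds a. With the same loss pattern in both arms:

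| s | m | a | Observed, 6 mg | Observed, weight-based |
|---|---|---|---|---|
| 10% | 10% | 10% | 25.0% | 6.5% |
| 10% | 50% | 5% | 23.3% | 5.9% |
| 20% | 100% | 5% | 20.4% | 5.0% |
| 30% | 100% | 5% | 18.3% | 4.4% |

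Observed mortality can be too high, right or too low, depending on quantities the documents do not give.

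**4. Sensitivity of the test to a few missed deaths.** Illustrative true data: 14/71 v 6/71. P-values are from the uncorrected chi-squared test.

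| Deaths missed (6 mg, weight-based) | Analysed data | Rates | p |
|---|---|---|---|
| none | 14/71 v 6/71 | 19.7% v 8.5% | 0.054 |
| 1 and 2 | 13/70 v 4/69 | 18.6% v 5.8% | 0.022 |
| 1 and 1 | 13/70 v 5/70 | 18.6% v 7.1% | 0.043 |
| 2 and 1 | 12/69 v 5/70 | 17.4% v 7.1% | 0.065 |

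Three missing is 3/142 = 2.1%, below the threshold. By Fisher's exact test, the first two rows give p = 0.089 and p = 0.036.

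**5. What complete follow-up would give.** If vital status is known for all 71 per arm, power at the planned rates is 84.3%, against 80.3% at 64 per arm.

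**The case against.** **The direction is not established.** A reader might infer that deaths will be lost and mortality therefore understated. The documents do not support that. Living patients also fail to respond, deaths in hospital are all known, and step 3 shows observed mortality rising under a plausible loss pattern. This objection stands: the claim is risk of selective loss, not demonstrated understatement.

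**Silence is not prohibition.** A reader might also take section 20 to allow one call only, or to rule out a record search. It says neither. A relative could answer the phone, and a death on readmission could appear in the health-system record. Patients enrolled through a representative already have a proxy contact. All this stands and reduces the likely number of missed deaths. It does not supply a stated procedure, and for patients who consent for themselves no other contact is specified.

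**Discharge to hospice or a care facility.** It is tempting to say that these patients are the least likely to reply. The documents give no response rates by destination, so nothing here rests on that.

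**The illustration is chosen.** The base case lies next to the 5% boundary. The split of 1 and 2 is not proportional to 14 and 6, and a split nearer to proportional (2 and 1) leaves the conclusion unchanged. The example also assumes that no survivor is lost. If the planned 10% dropout (about 14 of 142) left outcomes missing, the 5% threshold would be passed and the sensitivity analysis would run. This stands: the figures show fragility to small numbers, not an expected effect.

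**Overlap with the missing-data rule.** Running the sensitivity analysis at every level of missingness would expose the uncertainty. It would not recover the deaths. Finding vital status prevents the missing data, which is a separate repair.

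**Conclusion.** The concern holds in limited form. Followed as written, the plan makes observation of the primary endpoint after discharge depend partly on the endpoint, and no other section supplies a source that does not need the patient's reply. Deaths between discharge and day 28 are at risk of being selectively missing. With fewer than 5% unknown, the analysis gives no warning.

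The size cannot be estimated from the documents. What can be said is that up to 7 unchecked unknowns stand against about 4 expected deaths in one arm, and that missing three deaths can move an illustrative p-value from 0.054 to either 0.022 or 0.065, depending only on which arm loses more. The bias may favour either arm. The conclusion rests on reading section 20 as the whole post-discharge procedure for vital status, since no other section describes one. Death can be established without the patient, so this weakness is avoidable and worth correcting.

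**What to change.** In section 20, separate vital status from the symptom survey:

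1. Record an alternate contact for every participant at consent, including those who consent for themselves.
2. At day 28, make the same health-system record check for all discharged patients in both arms. A recorded death by day 28 counts as dead; an encounter on or after day 28 counts as alive.
3. Where the record does not settle it, phone the patient, then the alternate contact or the receiving facility.
4. Use the email survey for symptoms only.
5. Record the source of vital status for each patient and report it by arm.

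Amend section 9 so that participation runs to day 28 for discharged patients as well.

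The cost is one contact field, one record check per discharged patient, some extra calls by existing staff, and a line in the consent form covering the record check and the alternate contact. No procedures on patients are added.

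### The two safety endpoints have no time window and no stated capture after discharge, so harm can be under-counted and, if length of stay differs between arms, compared unevenly.

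*Combined protocol and SAP*

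**What the plan says.** - **Endpoints.** Section 10 names two safety endpoints. One is "development of secondary bacterial or fungal infections that is objectively identified based on culture data"; the other is "clinically significant hyperglycemia requiring ICU stay or insulin drip". Neither has a time window there, in Section 4, in the data list of Section 11 or in the monitoring plan of Section 15.
- **Length of participation.** Section 9 says that an individual's participation "will be 28 days or until hospital discharge, whichever occurs first".
- **Contact after discharge.** Section 20 provides for patients who leave before day 28: "a survey will be sent out via email using REDCap to determine primary endpoint and subjective symptoms". It adds: "For patients without access to email or who do not respond to the survey, a follow up phone call will be made". No further content is given for the call.
- **Data source.** Section 11: "Data will be obtained from the medical electronic records and tabulated in REDCap". It does not say whether records made after discharge are included. Section 16 mentions following the record over time only for patients who withdraw, and only if they agree.
- **Treatment.** Section 11: "The duration of treatment in both arms will be a total of 10 days of steroids or until discharge, whichever comes first".
- **Expected harms.** Section 17, where the list also covers fungal infection: "Potential risks for the patients in the higher dexamethasone dose group include but are not limited to higher risk of hyperglycemia, delirium and bacterial".
- **Length of stay.** Hospital stay is a secondary outcome compared between arms (Sections 4, 10 and 12).

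**The concern.** Death and symptoms are fixed at day 28 and have a stated route for reaching discharged patients. The two safety endpoints have neither. If Sections 9 and 20 are followed literally, each patient's time at risk for a recorded infection is the length of stay. That is set after randomization, and the higher dose may change it.

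Two things are at stake. Infections that appear after discharge could go uncounted in both arms. And if one arm goes home sooner, its harm would be counted over a shorter period than the other's. The benefit-risk statement would then set 28-day mortality against harm seen mostly in hospital. The monitoring committee, which assesses the same two events at 20, 50 and 100 patients (Section 15), would work from the same incomplete counts.

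**Working it through.** **What the plan's figures can settle.** The documents give no infection rate, no hyperglycemia rate, no expected stay and no figure for safety capture. The one design calculation, 64 per arm for 23.3% v 5.9% mortality, reproduces (80.3% power, two-sided 5%, no continuity correction). This point does not affect it.

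**Reading the sections together.** Section 9 ends participation at discharge. Section 20 has a contact after discharge. The two conflict, and neither extends safety follow-up. Section 12 uses methods that allow for censoring for the duration outcomes, but names no analysis for the two safety endpoints. So nothing in the analysis plan allows for unequal observation time.

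**Illustration 1: equal true risk (all inputs assumed).** Let the true 28-day risk be 10% in both arms, with constant hazard and capture ending at discharge.

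- Daily hazard h = −ln(1 − 0.10)/28 = 0.00376.
- Observed risk = 1 − exp(−h × stay).
- Stay of 10 days: 3.7%. Stay of 7 days: 2.6%. Ratio 0.70.
- Per 71 patients: 2.6 v 1.8 events seen, against 7.1 true events in each arm. About 63% and 74% are missed.
- Equal stays of 10 days: 3.7% in both arms, ratio 1.0. Events are lost but there is no bias between arms.
- If the hazard after day 10 is a quarter of the earlier one, stays of 10 v 7 days capture 7.0% v 5.0% of the 10%, ratio 0.71.

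**Illustration 2: higher dose truly worse (all inputs assumed).** Hazards are 1.0%/day (standard) and 1.5%/day (higher dose). Every patient in an arm has the same stay, counted from randomization, and deaths are ignored. Stays are at most 10 days, so days on drug equal days in hospital.

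- Standard arm at 28 days: 1 − exp(−0.28) = 24.4%.
- Higher dose, excess throughout 28 days: 1 − exp(−0.42) = 34.3%.
- Higher dose, excess on drug only, 7-day stay: 1 − exp(−(7 × 0.015 + 21 × 0.010)) = 1 − exp(−0.315) = 27.0%.
- Higher dose, excess on drug only, 8-day stay: 1 − exp(−(8 × 0.015 + 20 × 0.010)) = 1 − exp(−0.32) = 27.4%.
- Seen in hospital, 10 v 7 days: 1 − exp(−0.10) = 9.5% v 1 − exp(−0.105) = 10.0%.
- Seen in hospital, 9 v 8 days: 1 − exp(−0.09) = 8.6% v 1 − exp(−0.12) = 11.3%.

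| Stay, standard v higher dose | Excess hazard lasts | True difference | Difference seen |
|---|---|---|---|
| 10 v 7 days | on drug only | 2.6 points | 0.5 points |
| 9 v 8 days | on drug only | 3.0 points | 2.7 points |
| 10 v 7 days | all 28 days | 9.9 points | 0.5 points |
| 9 v 8 days | all 28 days | 9.9 points | 2.7 points |

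**Direction.** With equal hazards of 1.0%/day, stays of 10 v 7 days show 9.5% v 6.8%, an apparent advantage for the higher dose. If the stays are reversed, the same figures become an apparent harm.

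**The case against.** The strongest reply is that not being asked is not the same as not being captured. The survey is not the stated source for these endpoints; the electronic record is. All seven recruiting hospitals belong to one health system (Section 6), so a readmission there could be visible. A patient's reply to a survey also cannot establish a culture result. This stands. A reader might infer that a readmission on day 15 with a positive culture would certainly be scored as no event, but the documents do not say so. They leave open whether anyone looks.

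A reader might also infer that the arm discharged sooner will look safer. That needs a difference in stay, and no expected stay is given. Death shortens observation too. Under the assumed mortality of 23.3% v 5.9%, the extra survivors on the higher dose could be observed longer, which pushes the other way.

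The size also depends heavily on what happens after discharge. The 9.9-point harm requires the excess to run for 28 days, although study drug stops by day 10 or at discharge. If the hazard falls to 0.1%/day at home in both arms, stays of 10 v 7 days give true risks of 1 − exp(−0.118) = 11.1% v 1 − exp(−0.091) = 8.7%. That is a real 2.4-point advantage, against 9.52% − 6.76% = 2.8 points seen, so there is little distortion.

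Finally, hyperglycemia as defined needs an insulin drip or ICU care, so after discharge it can arise only on a return to hospital with study drug stopped. This half of the concern is weak.

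None of these replies supplies a common window or a stated record search.

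**Conclusion.** The concern holds in a limited form. Safety observation has no defined end, and the plan as written allows it to end at discharge. That would under-count events in both arms. It would bias the comparison only if stay differs by arm, and the direction would follow that difference. The documents do not fix the size: in the illustrations the distortion runs from slight (3.0 points seen as 2.7) to almost complete masking (9.9 seen as 0.5). All of those figures rest on assumed hazards and stays.

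The point rests mainly on infection. It should not be read as saying that all efficacy is followed to day 28 and harm is not: only death and symptoms carry a day-28 time point, other outcomes such as ICU admission and ventilation also lack a window, and all-cause mortality would include fatal harm. The primary endpoint and sample size are unaffected. The change should be made because the benefit-risk comparison depends on it and missed events may be hard to recover later.

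**What to change.** 1. Define both safety endpoints from randomization to day 28 for every patient, in or out of hospital.
2. State that the health-system record will be searched to day 28 for readmissions, cultures, and insulin drip or ICU care for glucose. This is the main repair.
3. Add questions on readmission, emergency visits and treated infection to the planned survey and phone call, to detect care outside the system.
4. Report in-hospital and 28-day counts by arm, with self-reported events separate from culture-confirmed ones.
5. Reconcile the end of participation in Section 9 with the contact after discharge in Section 20.

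The cost is a short amendment, a record check per patient and a few extra questions on a contact already planned. The downside is that some events from outside the system will rest on self-report. The sample size does not change.
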